GC2007 - A Multicenter, Randomized, Open-label Parallel Group Pilot Study to Evaluate Safety and Efficacy of High Dose Intravenous Immune Globulin (IVIG) plus Standard Medical							
Bioscience Industrial Group							

Appendix 5 Summary of Changes from Version 3.0 to Version 4.0

(Note: Administrative changes including minor administrative corrections are not included in Protocol Summary of Changes)

Sections	Change From: (Version 3.0, dated 30 Oct 2020) (Strikethrough is added to highlight deleted text)	Change To: (Version 4.0) (Underline is added to highlight new text)	Rationale:
Title Page	Not applicable	Study Number/Protocol Version Number: GC2007/Version 4.0	Added to identify the protocol and version number of this document.
Protocol Synopsis; Study Assessments and Procedures Section 4.2 Study Design and Plan Appendix 1 Schedule of Study Procedures; Footnote e	Not applicable	If an in-person visit is unable to be conducted for Day 15 or Day 29, the study site will make a phone call to the subject to obtain as much information as possible remotely (e.g., Ordinal Scale, clinical features key symptoms, supplementation oxygen use, SAEs and TEAEs, concomitant medications).	Added to allow the flexibility in obtaining study related data.
Section 7.2.5 Day 15 ^{±1} day – All Subjects	Not applicable	If an in-person visit is unable to be conducted for Day 15, the study site will make a phone call to the subject to obtain as much information as possible remotely (e.g., Ordinal Scale, clinical features key symptoms, supplementation oxygen use, SAEs and TEAEs, concomitant medications).	Added to allow the flexibility in obtaining study related data.

CONFIDENTIAL

Sections	Change From: (Version 3.0, dated 30 Oct 2020) (Strikethrough is added to highlight deleted text)	Change To: (Version 4.0) (Underline is added to highlight new text)	Rationale:
Section 7.2.7 Day 29+1 day – All Subjects	Not applicable	If an in-person visit is unable to be conducted for Day 29, the study site will make a phone call to the subject to obtain as much information as possible remotely (e.g., Ordinal Scale, clinical features key symptoms, supplementation oxygen use, SAEs and TEAEs, concomitant medications).	Added to allow the flexibility in obtaining study related data.
Section 8.3.9.1 Reporting of Serious Adverse Events	Grifols Global Pharmacovigilance Email: [REDACTED] FAX (back-up only): [REDACTED] (US/Canada) [REDACTED] (International)	Grifols Global Pharmacovigilance Email [REDACTED] FAX (back-up only): [REDACTED] (US/Canada) [REDACTED] (International)	Updated to remove the US/Canada fax number and to keep only International fax number.
Section 10 Direct Access to Source Data/documents	If access to source documentation is restricted due to Covid-19 emergency, source data verification will occur at the earliest practicable time when the monitor can have safe and direct access to the documentation. No remote source data verification will be carried out.	If access to source documentation is restricted due to Covid-19 emergency, source data verification will occur at the earliest practicable time when the monitor can have safe and direct access to the documentation. No remote source data verification will be carried out.	Removed to allow remote Source Data Verification when appropriate and feasible to ensure data integrity, quality, and safety of the participants.
Section 11 Quality Control and Quality Assurance	If access to the study center is restricted due to Covid-19 emergency, only remote monitoring will occur until restrictions are lifted. On-site visits will occur as soon as it is possible to safely access the site and have direct access to the documentation. No remote source data verification will be carried out.	If access to the study center is restricted due to Covid-19 emergency, only remote monitoring will occur until restrictions are lifted. On-site visits will occur as soon as it is possible to safely access the site and have direct access to the documentation. No remote source data verification will be carried out.	Removed to allow remote Source Data Verification when appropriate and feasible to ensure data integrity, quality, and safety of the participants.

GRIFOLS	Number	BiG-CL-PRT-000020	Version	4.0	Status	Effective	Effective Date	19-Jul-2021
	GC2007 - A Multicenter, Randomized, Open-label Parallel Group Pilot Study to Evaluate							
Bioscience Industrial Group	Safety and Efficacy of High Dose Intravenous Immune Globulin (IVIG) plus Standard Medical							

Sections	Change From: (Version 3.0, dated 30 Oct 2020) (Strikethrough is added to highlight deleted text)	Change To: (Version 4.0) (Underline is added to highlight new text)	Rationale:
Section 13.1 Data Handling	Remote source data verification will not be carried out.	Remote source data verification will not be carried out be allowed when appropriate and feasible to ensure data integrity, quality, safety of the participants and patients' confidentiality data is not compromised.	Updated to allow remote Source Data Verification when appropriate and feasible to ensure data integrity, quality, safety of the participants and patients' confidentiality data is not compromised.

CONFIDENTIAL

## LIST OF ABBREVIATIONS

Abbreviation	Definition
ADR	Adverse drug reaction
AE	Adverse event
ANOVA/ANCOVA	Analysis of variance/covariance
ARDS	Acute respiratory disease syndrome
ATC	Anatomical, Therapeutic, and Chemical
BMI	Body mass index
CI	Confidence interval
CIF	Cumulative Incidence Function
COVID-19	Coronavirus disease 2019
eCRF	Electronic Case Report Form
CRP	C-reactive protein
ECMO	Extracorporeal Membrane Oxygenation
FEU	Fibrinogen Equivalent Units
ICU	Intensive care unit
IgG	Immunoglobulin G
IgM	Immunoglobulin M
IL	interleukin
IP	Investigational product
ITT	Intention to treat
IV	Intravenous
KM	Kaplan-Meier
LS	Least-Squares
IVIG	Intravenous immune globulin
MedDRA	Medical Dictionary for Regulatory Activities
MMRM	Mixed-effects model for repeated measures
NAT	Nucleic acid amplification technology
NCI	National Cancer Institute
NEWS	National Early Warning Score
NIH	National Institutes of Health

Abbreviation	Definition
PCR	Polymerase chain reaction
PI	Principal Investigator
PP	Per Protocol
PT	Preferred term
RT-PCR	Reverse transcriptase PCR
SAE	Serious adverse event
SAF	Safety
SaO 2	Arterial oxygen saturation
SAP	Statistical analysis plan
SARS-CoV-2	Severe acute respiratory syndrome coronavirus 2
SISRC	Study-Independent Safety Review Committee
SMT	Standard medical treatment
SOC	System organ class
SOFA	Sequential Organ Failure Assessment
SpO 2	Oxygen Saturation by pulse oximetry
TEAE	Treatment-emergent adverse event
TNF- $\alpha$	tumor necrosis factor- $\alpha$
WHO	World Health Organization

## SAP REVISIONS

Version 1.0 of the SAP was finalized based on Protocol version 3.0 (30 October 2020). The following table details subsequent changes made to the SAP.

Revision History			
SAP Version #	SAP Section	Modification	Description and Rationale
2.0	5.6	Added “or Preferred”	The COVID-19 specific, potentially disease modifying medications may be identified by Preferred term.
2.0	6.2	Added "Duration of ICU stay (Actual and Medical Equivalence)" analysis section  Added "Duration of Hospitalization (Actual and Medical Equivalence)" analysis section  Added age and gender as covariates to the MMRM model	Added to reflect the planned analysis.  Added to reflect the planned analysis.  Added to reflect the planned analysis.

## 1. INTRODUCTION

This statistical analysis plan (SAP) is based on the Protocol # GC2007 Version 3.0, dated 30 October, 2020, and titled “A Multicenter, Randomized, Open-label Parallel Group Pilot Study to Evaluate Safety and Efficacy of High Dose Intravenous Immune Globulin (IVIG) plus Standard Medical Treatment (SMT) versus SMT alone in Subjects with COVID-19 Requiring Admission to the Intensive Care Unit.” See the study protocol for full details.

This document details the statistical methods planned to perform the interim and final analyses of the study.

## 2. OBJECTIVES AND ENDPOINTS

### 2.1 Objectives

#### 2.1.1 Primary Efficacy Objective

To determine if high dose IVIG plus SMT can reduce all-cause mortality versus SMT alone in hospitalized subjects with COVID-19 requiring admission to the intensive care unit (ICU) through Day 29.

#### 2.1.2 Secondary Efficacy Objectives

To compare high dose IVIG plus SMT versus SMT alone with regard to clinical efficacy as assessed by clinical severity, duration of hospital and ICU stay, dependency on oxygen and ventilatory support, and clinical response criteria including National Early Warning Score (NEWS), clinical status scale, and Sequential Organ Failure Assessment Score (SOFA) through Day 29 in hospitalized subjects ill with COVID-19 requiring admission to the ICU.

#### 2.1.3 Exploratory Efficacy Objectives

The exploratory objectives of the study are:

- To evaluate the effect of high dose IVIG plus SMT versus SMT alone with regard to quantitative severe acute respiratory syndrome coronavirus 2 (SARS-CoV-2) viral load and anti-SARS-CoV-2 antibodies in hospitalized subjects with COVID-19.
- To evaluate whether high dose IVIG plus SMT versus SMT alone reduces the frequency of hyperinflammation based on a pre-specified biochemical definition through Day 29.
- To evaluate cytokine profile changes from baseline for high dose IVIG plus SMT versus SMT alone through Day 29.

#### 2.1.4 Safety Objective

To determine the safety and tolerability profile through Day 29 of high dose IVIG plus SMT versus SMT alone in hospitalized subjects with COVID-19.

## 2.2 Endpoints

### 2.2.1 Primary Efficacy Endpoint

The primary efficacy endpoint is all-cause mortality rate through Day 29.

### 2.2.2 Secondary Efficacy Endpoints

The secondary efficacy endpoints include the following:

- Time to actual ICU discharge: defined as duration of ICU stay from Day 1 through Day 29
  - Additionally, time to a medical equivalence of ICU discharge will be recorded and analyzed (defined as the time point when the patient no longer requires ICU level care, ie, not requiring invasive mechanical ventilation, or intensive monitoring such as arterial line or central line placement, administration of IV vasopressors to support blood pressure, or O2 supplementation greater than that delivered by nasal cannula)
- Duration of mechanical ventilation from Day 1 through Day 29
- Time to actual hospital discharge: defined as duration of hospitalization from Day 1 through Day 29
  - Additionally, time to a medical equivalence of hospital discharge will be recorded and analyzed (defined as the time point when the patient no longer requires supplemental oxygen and no longer requires ongoing medical care [yet may not be discharged from hospital for social or quarantine reasons])
- Duration of any oxygen use Day 1 through Day 29
- Absolute value and mean change from baseline in the Ordinal scale Day 1 through Day 29

The Ordinal scale is as follows:

- 1) Death;
- 2) Hospitalized, on invasive mechanical ventilation or extracorporeal membrane oxygenation (ECMO);
- 3) Hospitalized, on non-invasive ventilation or high flow oxygen devices;
- 4) Hospitalized, requiring supplemental oxygen;
- 5) Hospitalized, not requiring supplemental oxygen;
- 6) Not hospitalized, limitation on activities;
- 7) Not hospitalized, no limitations on activities.

- Proportion (percentage) of subjects in each severity category of the 7-point Ordinal scale at Day 15 and Day 29
- Number of subjects who develop Acute Respiratory Distress Syndrome (ARDS) overall and distribution by severity through Day 29
- Change from baseline in SOFA score at Day 5, Day 15, and Day 29

- Assessment of Clinical Severity: Change in NEWS from baseline (Day 1 through Day 29).  
The NEWS has demonstrated an ability to discriminate patients at risk of poor outcomes. This score is based on 7 clinical parameters (respiration rate, oxygen saturation, any supplemental oxygen, temperature, systolic blood pressure, heart rate, level of consciousness [Alert, Voice, Pain, Unresponsive]).
- Time to clinical response: NEWS  $\leq 2$  maintained for 24 hours, Day 1 through Day 29

### **2.2.3 Exploratory Efficacy Endpoints**

Exploratory efficacy endpoints include:

- Change from baseline in quantitative SARS-CoV-2 viral load by nucleic acid amplification technology (NAT) or polymerase chain reaction (PCR; real-time reverse transcriptase [RT]-PCR) to Days 5, 15, and 29
- Change from baseline in quantitative anti- SARS-CoV-2 immunoglobulin M (IgM) and IgG antibodies to Days 5, 15, and 29
- Proportion of subjects with evidence of hyperinflammation on Day 1, Day 5, Day 15, and Day 29 defined as:
  - a) Lymphocyte counts  $<1000$  cells/ $\mu$ L, AND
  - b) Two of the following 4 criteria:
    - i) Ferritin  $> 500$  ng/mL,
    - ii) LDH  $> 300$  U/L,
    - iii) D-Dimers  $> 1000$  ng/mL (fibrinogen equivalent units [FEU]) or  $> 2$  times upper normal limit,
    - iv) C-reactive protein (CRP)  $> 70$  mg/L
- Change from baseline in cytokine profile (interleukin (IL)-1 $\beta$ , IL-10, IL-6, IL-8 IL-2, interferon  $\gamma$ , and tumor necrosis factor- $\alpha$  [TNF- $\alpha$ ]) to Days 5, 15, and 29

### **2.2.4 Safety Endpoints**

The safety endpoints include:

- Cumulative incidence of treatment-emergent serious adverse events (SAEs) and potentially related SAEs through Day 90 Phone Check
- Cumulative incidence of Grade 3-5 treatment-emergent adverse events (TEAEs) and potentially related severe TEAEs through Day 29 as defined in the Common terminology Criteria for Adverse Events (CTCAE), US Department of Health and Human Services, National Institutes of Health (NIH), and National Cancer Institute (NCI)
- Cumulative incidence of all TEAEs and potentially related TEAEs through Day 29

### 3. INVESTIGATIONAL PLAN

#### 3.1 Study Design

This is a prospective, multi-center, randomized (1:1), open-label, pilot study of high dose IVIG plus SMT versus SMT alone in subjects with COVID-19 who are hospitalized and require ICU admission. The first 6 subjects randomized will be staggered with an interval of no less than 1 week between subjects. If there are no definitely related SAEs reported 1 week after the randomization of the 6th subject, competitive enrollment would ensue thereafter. If a definitely related SAE were to be reported among these 6 subjects, the Study-Independent Safety Review Committee (SISRC) would carefully review and evaluate the case and make appropriate recommendations with regard to study status.

In this study, symptomatic subjects with positive PCR (RT-PCR) or other FDA-approved or regulatory-authority-approved diagnostic assay for SARS-CoV-2 in any specimen during the current hospital admission prior to randomization will receive SMT or SMT plus a net total dose of IVIG of 2 g/kg (body weight) administered in divided doses over 4 to 5 consecutive days at the Principal Investigator (PI)'s discretion. The maximum dose will be capped at 160 g (equivalent to body weight of 80 kg).

[figure not shown]
Specifically, subjects randomized to combination high dose IVIG will receive the first intravenous (IV) infusion of IVIG on Day 1. The total net dose of 2 g/kg body (capped at a maximum of 160 g for subjects weighing more than 80 kg) will be administered in divided doses over consecutive days. At the discretion of the PI, the 2 g/kg net total dose may be divided either into (a) infusions of 500 mg/kg body weight over 4 days OR (b) 400 mg/kg body weight over 5 days.

Approximately 100 subjects (who meet the inclusion/exclusion criteria specified in Protocol Sections 5.1 & 5.2) will be randomized in a 1:1 (IVIG plus SMT : SMT alone) ratio with an interim analysis after 50 subjects (approximately 25 per group). There will be no interruption in study conduct during interim analysis as this simply represents sponsor safety due diligence.

All subjects will be followed daily through Day 10. After Day 10, if subjects are discharged from the hospital, evaluations at Day 15 and 29 are required. Berlin criteria for ARDS and SOFA score will be assessed on Day 1, 5, 15, and 29. Subjects remaining hospitalized will be followed daily through Day 29. Phone Checks will occur at Day 60 and Day 90 for vital status (living or deceased), any hospital re-admissions or serious/non-serious AEs after the Day 29 Final Clinic Visit. See Appendix A for the Schedule of Events.

Clinical trial finalization will coincide with the last study visit of the last subject enrolled in the clinical trial. For an individual subject, end of study for the purposes of determining disposition and successful study completion is the Day 29/Final Clinic Visit performed at the scheduled on-study timeframe.

An overview of the study design is presented below:

## 3.2 Treatment

### 3.2.1 Randomization Scheme and Treatment Arm Assignment

Subjects will be randomized 1:1 to receive either combination treatment with Gamunex-C plus SMT or SMT alone. A central randomization will be used for this study. A randomization list containing the randomization numbers and the corresponding randomized treatment assignments will be generated and be stored in a secured area that is only accessible to the randomization team.

### 3.2.2 Blinding

Not applicable as this is an open-label study.

### 3.2.3 Dosing Schedule

During this clinical trial, subjects randomized to receive combination Gamunex-C plus SMT will receive a total dose of 2 g/kg body weight (capped to a maximum of 160 g for subjects weighing more than 80 kg) in divided doses at the discretion of the PI over 4 or 5 days. The first IV infusion will be on Day 1.

### 3.2.4 Treatment Compliance

Reasons for any deviation from the administration of less than 100% of the investigational product (IP) dose must be recorded in the subject's medical records.

The investigator or designee is responsible for maintaining accurate records of Gamunex-C administered at his/her study center.

## 4. GENERAL CONSIDERATIONS FOR DATA ANALYSIS

Unless otherwise specified, continuous variables will be summarized using descriptive statistics (n, mean, standard deviation, median, minimum, and maximum). Categorical variables will be summarized showing the number and percentage of subjects within each category.

Summary results will be provided for each treatment group. All tabulations will be based on pooled data across centers.

All statistical tests will be two-sided and tested at the 5% level of significance.

Analyses will be performed using SAS for Windows statistical software, version 9.4 or higher (SAS, Cary, NC), except where other software may be deemed more appropriate. In the event that other software is used to perform some analyses, the details will be provided in the Clinical Study Report.

■ will perform all efficacy and safety analyses described in this SAP.

Subject data will be listed, sorted by treatment group and subject number. When applicable, listings will be additionally sorted by visit and assessment date/time.

#### **4.1 Data Quality Assurance**

Once all the source verification is complete, all queries are resolved, and the database has been updated appropriately, the database will be locked and made available to ■ Biostatistics for final analysis.

Data may be pulled by ■ Biostatistics for interim analysis at a time when source verification and query resolution is ongoing.

All SAS programs used to create analysis data sets, tables, and listings are double programmed. The SAS outputs will be compared and the programs will be updated until the outputs match.

#### **4.2 Analysis Populations**

The following three analysis populations will be defined for this study:

The intent-to-treat (ITT) population is defined as all subjects who are randomized. All efficacy analyses will be carried out using the ITT population based on the randomized treatment.

The Per-Protocol (PP) population is defined as the subset of subjects included in the ITT population who do not present major protocol violations which might have an impact on the primary efficacy endpoint, and complete at least 80% of the IP. The primary efficacy analyses will be carried out using the PP population if different from the ITT population.

The Safety (SAF) population for the combination arm is defined as the subset of subjects who receive at least any amount of Gamunex-C in addition to SMT. The SAF population for the SMT alone arm will include all subjects randomized to this arm, because by definition SMT is universally provided and hence all randomized subjects would have received SMT. All safety analyses will be carried out using the SAF population based on the treatment actually received rather than randomized treatment.

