5.3.4 Follow-up of Subjects Withdrawn from Study

For subjects administered any amount of IP (infusion) who discontinue the clinical trial, and for subjects randomized to SMT alone, details for follow-up are delineated below.

For subjects who withdraw from the clinical trial (excluding screen failures), study procedures and assessments scheduled for the Day 15 Visit will be performed at the time of withdrawal, during an unscheduled visit at the time of withdrawal. In addition, to assure major clinical outcomes are adequately captured as a measure of overall safety, these subjects will be asked to return for their chronological Day 29 Clinic Visit (ie, 28 days after Day 1 baseline), unless the unscheduled visit is within 4 days of their chronological Day 29 visit, and provided that they or their legally acceptable representative have not withdrawn consent. At the chronological Day 29 Clinic Visit, all assessments will be performed *except for* central laboratory testing: cytokine panel, respiratory sample for quantitative measurement of SARS-

GRIFOLS Bioscience Industrial Group	Number	BLG-CL-PRT-000020	Version	4.0	Status	Effective	Effective Date	19-Jul-2021	44 of 91
	GC2007 - A Multicenter, Randomized, Open-label Parallel Group Pilot Study to Evaluate Safety and Efficacy of High Dose Intravenous Immune Globulin (IVIG) plus Standard Medical Treatment (SMT) versus SMT alone in								

CoV-2 viral load (obtained via nasopharyngeal swab), and quantitative measurement of IgM and IgG antibodies, which are not required for these subjects at chronological Day 29 for premature withdrawals. These subjects will also have Phone Checks at Day 60 and Day 90 for vital status (living or deceased), and any hospital re-admissions or serious/non-serious adverse events after the Day 29 Final Clinic Visit.

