8.3.4 Assessment of Causality of Adverse Event

The investigator is required to provide a causality assessment for each AE reported to the sponsor. The assessment of the causal relationship of an AE to the administration of IP must be a clinical decision based on all available information at the time of the completion of the CRF and/or SAE Report Form. The sponsor will consider the investigator's causality assessment and also provide its own assessment.

Causal relationship to the IP will be established according to medical judgment on whether there is a **reasonable possibility of a causal relationship between the AE and the IP administration.**

The investigator must determine and classify the AE causality according to the following categories:

Unrelated/Not related: there is not a reasonable possibility of causal relationship between the AE and the IP.

Possibly related: there is evidence to suggest a causal relationship between the IP and the AE.

Definitely related: there is a reason to conclude that the IP caused the AE.

Criteria to assess the causal relationship should take into account of the following conditions: 1) a plausible temporal sequence from the IP administration to the AE onset; 2) whether the event follows a known response pattern to the suspected treatment; 3) whether the AE could be reasonably explained by the subject's clinical state, comorbidities, or concomitant medications, as well as 4) the occurrence of improvement on stopping/reducing the treatment (positive dechallenge) and/or reappearance of the event on repeated exposure (positive rechallenge).

For expedited safety reporting purposes, AEs assessed as either "definitely related" or "possibly related" will be considered POTENTIALLY RELATED or just RELATED.

Any AE reported prior to the first administration of the IP will be considered a non-treatment-emergent AEs and causal relationship will always be "Unrelated/Not related."

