9 STATISTICS

9.1 Statistical Methods

Descriptive statistics will include the number of non-missing observations, mean, standard deviation (SD), median, minimum, and maximum values for the continuous/quantitative data or absolute and relative frequency counts and percentages for categorical/qualitative data. All statistical tests will be 2-sided at a significance level of 0.05.

An interim analysis will be conducted after 50 subjects (approximately 25 per group) for safety variables through Day 29. Due to the exploratory nature of this phase 2 study, the multiplicity adjustments will not be considered; full details will be described in the statistical analysis plan. This interim evaluation simply represents Sponsor safety due diligence.

There will be 3 analysis populations in this study; 2 populations for efficacy assessments and 1 population for safety evaluation.

The intention to treat (ITT) population is defined as all subjects who are randomized. The ITT population will be used for all efficacy analyses.

The Per-Protocol (PP) population is defined as the subset of subjects included in the ITT population who do not present major protocol violations which might have an impact on the primary efficacy endpoint, and complete at least 80% of the IP. The primary efficacy analyses will be carried out using the PP population if different from the ITT population.

The Safety population is defined as the subset of subjects who receive at least any amount of IVIG plus SMT or SMT alone. Safety analyses will be based on the Safety population.

The primary efficacy analysis will be carried out on the ITT population and repeated on the PP population (if different from the ITT population) by Fisher's exact test or Chi-square test. Secondary and exploratory efficacy analyses will be analyzed by means of Kaplan-Meier survival estimates and curves and compared between treatment groups by means of the Log-rank test for time to event variables, analysis of covariance (ANCOVA) or Student's t test for normally-distributed variables or Wilcoxon rank-sum test for non-normally-distributed variables. Detailed data handling and evaluation procedures and details of the interim reviews will be described in the Statistical Analysis Plan (SAP). The SAP may include exploratory analyses of various aspects of SMT inclusive of different interventional strategies and evolving treatment modalities.

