#### 7.2.1 Treatment-emergent Adverse Events

For summary purposes, AEs will be classified as treatment-emergent AEs (TEAEs) or non-treatment-emergent AEs (non-TEAEs) depending on the comparison of AE onset date/time with the date of randomization. A TEAE will be defined as an AE which occurred on or after the date of randomization. For adverse events with incomplete start dates/times, the same imputation algorithm for missing or partial date/time information as described in Section 5.6 will be used for the determination of an AE being treatment emergent or not. Briefly, the unknown portions of an AE onset date/time will be imputed to the latest possible before being compared to the date of randomization.

Non-TEAEs will be summarized separately from TEAEs by SOC and PT for each treatment group and overall.

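### The SAP's safety set requires an infusion in the IVIG arm but no exposure in the SMT-alone arm, so subjects randomised to IVIG and never infused leave the IVIG safety column

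*SAP*

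**What the plan says.** SAP 4.2 builds the safety set separately for each arm. The combination-arm set is the "subset of subjects who receive at least any amount of Gamunex-C in addition to SMT". For control, "The SAF population for the SMT alone arm will include all subjects randomized to this arm", on the reasoning that everyone gets SMT. The same paragraph says safety analyses are "based on the treatment actually received rather than randomized treatment". SAP 7 runs every safety summary on this set, without formal testing, and SAP 8 applies the same methods to the interim look after 50 subjects.

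Protocol 9.1 defines the set in one phrase for both arms: the "subset of subjects who receive at least any amount of IVIG plus SMT or SMT alone".

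The documents give two start points for treatment-emergent events. SAP 7.2.1: "A TEAE will be defined as an AE which occurred on or after the date of randomization". Protocol 8.3.4: "Any AE reported prior to the first administration of the IP will be considered a non-treatment-emergent AEs".

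On withdrawals, Protocol 5.3.4 opens with a scope sentence, "For subjects administered any amount of IP (infusion) who discontinue the clinical trial, and for subjects randomized to SMT alone", which does not name subjects randomised to IVIG and never infused. Its next sentence applies the withdrawal visit to everyone who withdraws, screen failures excepted.

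**The concern.** In the control column, follow-up for events starts at randomisation. In the IVIG column it also starts at randomisation, but only for subjects who remain alive and in the study until the first infusion begins. An SMT-alone subject with an SAE a few hours after randomisation is counted. An IVIG-arm subject with the same event at the same time, and no infusion, is not counted in the IVIG column.

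The documents allow for such subjects. Protocol 5.3 permits withdrawal before infusion, and Protocol 6.1 and 7.2.2 make the start of infusion conditional on a blood-pressure reading taken shortly beforehand. SAP 6.1 plans a sensitivity analysis of the primary endpoint when actual and randomised treatment differ. There is no counterpart for safety.

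Where the subject goes is also unsettled. The arm-specific sentences of SAP 4.2 leave the subject out of both columns. The actual-treatment rule, read with Protocol 9.1, can place the subject in the SMT-alone column. Two programmers could follow the text and produce different tables.

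At stake is the between-arm reading of SAEs, Grade 3 or higher TEAEs and TEAEs leading to death, at the end and at the interim safety look.

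**Working it through.** The plan gives no event rate and no expected number of never-infused subjects, so it has no figure of its own to reproduce. Only the allocation can be checked: about 100 subjects at 1:1 is 50 per arm, and the interim at 50 is 25 per arm (Protocol 4.2).

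**Inputs.** n = 50 per arm is from the protocol. The rest is assumed: e = 20 subjects with an SAE in each arm, so the true difference is zero; k IVIG-arm subjects never infused, of whom h have an SAE. The worst case is h = k.

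**Formulas.**
- IVIG column, either reading: (e - h)/(n - k)
- SMT-alone column if never-infused subjects are excluded: e/n
- SMT-alone column if they are moved to control: (e + h)/(n + k)

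**Results at n = 50, e = 20.**

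| k | h | IVIG | SMT alone, excluded | Difference | SMT alone, moved | Difference |
|---|---|---|---|---|---|---|
| 1 | 1 | 19/49 = 38.8% | 20/50 = 40.0% | -1.2 | 21/51 = 41.2% | -2.4 |
| 3 | 3 | 17/47 = 36.2% | 20/50 = 40.0% | -3.8 | 23/53 = 43.4% | -7.2 |
| 3 | 0 | 20/47 = 42.6% | 20/50 = 40.0% | +2.6 | 20/53 = 37.7% | +4.8 |

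The last row shows the reversal. The IVIG rate falls when h/k exceeds e/n and rises when h/k is below it. The direction therefore depends on whether never-infused subjects have more events than the rest of their arm.

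**Other assumed event rates.** With k = h = 3 and true rates from 20% (10/50) to 40% (20/50), the difference runs from -5.1 to -3.8 points if excluded and from -9.6 to -7.2 if moved.

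**Only half with an event.** With e = 15, k = 4 and h = 2: 13/46 = 28.3% against 15/50 = 30.0%, or -1.7 points if excluded.

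**Interim.** With n = 25, e = 8 and k = h = 2: 6/23 = 26.1% against 8/25 = 32.0% (-5.9), or against 10/27 = 37.0% (-11.0).

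**Chance that the case arises.** If each of 50 IVIG-arm subjects has probability q of never being infused, the chance of at least one is 1 - (1 - q)^50: 39% at q = 1%, 64% at 2%, 92% at 5%. These values of q are assumed.

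**After the change.** With all randomised subjects kept in their randomised arm, the table shows 20/50 against 20/50, a difference of zero for any k and h.

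**The case against.** An exposure-based, as-treated safety set is a common convention. First infusion is planned for Day 1, so few subjects may be affected, and the illustration assumes the worst case. The shifts are below the sampling error: at 40% and 50 per arm the standard error of a difference is the square root of 2 x 0.4 x 0.6/50, about 9.8 points. Safety is descriptive only. Nor are the events hidden: SAEs are collected from consent (Protocol 8.3.9), the safety committee reviews all TEAEs and SAEs (Protocol 8.5), every AE is listed (SAP 7.2.5), and the disposition table shows the size of each population (SAP 5.1). All of this stands and limits the weight of the point. It does not settle where these subjects go, and a listing does not correct a between-arm percentage.

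A reader might also infer four stronger things, which the documents do not support:

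- **That early deaths vanish from the IVIG arm.** They can leave the safety tables only. The primary mortality analysis uses all randomised subjects by randomised arm (SAP 4.2, 6.1), so a death before infusion stays in the IVIG arm there.
- **That never-infused IVIG subjects lose follow-up.** Only the opening sentence of Protocol 5.3.4 omits them; the next covers all withdrawals except screen failures. If vital status were nevertheless missing, SAP 6.1 counts it as death, which would go against IVIG.
- **That the bias always favours IVIG.** It reverses if the never-infused subjects are event-free.
- **That infusion waits on baseline assessments after randomisation.** Protocol 7.2.2 and Appendix 1 place randomisation after those assessments. The blood-pressure condition is mainly a source of delay.

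**Conclusion.** The asymmetry in SAP 4.2 is real and carries into the final and interim safety tables. Subjects randomised to IVIG and never infused leave the IVIG column under either reading, and under one of them their events are added to control. IVIG looks safer if these subjects have more early events than the rest of their arm, as when death or deterioration is what prevents the infusion.

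Under the assumed figures (50 per arm, 20 with an SAE in each, an SAE in every never-infused subject), the artificial difference is -1.2 or -2.4 points for one such subject and -3.8 or -7.2 for three. The documents give neither the event rate nor the number never infused, and that number may be small. The conclusion is confined to the safety tables; the ITT mortality comparison does not change.

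The conflicting treatment-emergent start points are a related defect. The protocol's wording would also drop pre-infusion events of infused subjects, and it cannot be applied to SMT-alone subjects, who never receive the product. SAP 7.2.1 does give a usable rule for the summaries, so the two texts need reconciling. The Protocol 5.3.4 wording is a tidy-up only.

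**What to change.** 1. **SAP 4.2, 7.2.5 and 8.** Present the between-arm tables of SAEs, Grade 3 or higher TEAEs and TEAEs leading to death on all randomised subjects, by randomised arm, counting from randomisation, at both the interim and the final analysis. Keep the Gamunex-C-exposed set for exposure, infusion and adverse drug reaction tables. State explicitly where a subject randomised to IVIG but never infused is placed in any remaining safety-set table.
2. **Protocol 8.3.4 and SAP 7.2.1.** Reconcile the two treatment-emergent start points so that one rule works in both arms.
3. **Protocol 5.3.4.** Reconcile the opening sentence with the one after it, so that the stated scope covers all randomised subjects.

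The cost is a few extra tables and short wording changes. No new data are needed, since SAEs are already recorded from consent. The small downside is an IVIG denominator that includes a few unexposed subjects; the exposure table can show how many.
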